1. PROTOCOL SUMMARY

Title:

FiO₂ Closed-Loop Control Using the ZOLL 731 Series Ventilator.

Précis:

A randomized, multicenter trial involving critically-ill patients comparing conventional, manual control of inspired oxygen (FiO₂) within a target range, with a computer-controlled, closed-loop FiO₂ delivery using an FDA-cleared continuous ventilator.

Objectives:

The objective of this study is to demonstrate that physiologic closed-loop control (PCLC) is at least as safe and effective as manual control in keeping hemoglobin oxygen saturation (SpO₂) within the target range of 92 to 96%.

The primary efficacy outcome is the relative duration as defined by the total duration of minutes with SpO₂ within the target range of 92 to 96% divided by 720 minutes (the planned duration of the study). Similarly the relative duration for the primary safety outcome is defined as the total duration of time that the SpO₂ level at or above 88% divided by 720 minutes.

Hypothesis:

We plan to conduct a 2-state statistical test: non-inferiority followed by a superiority test. Demonstration of non-inferiority for both the effectiveness and safety endpoints is required for study success.

Primary effectiveness for non-inferiority: The use of PCLC to maintain oxygen saturation (SpO₂) within the target range of 92 to 96%, as measured by the relative duration, is not inferior to the manual control (MC).

Secondary effectiveness for non-inferiority: The use of PCLC to maintain oxygen saturation (SpO₂) within the target range of 92 to 96% when FiO₂ > 21% and SpO₂ ≥ 92% when FiO₂ = 21%, as measured by the relative duration, is not inferior to the manual control (MC) group.

Primary effectiveness for superiority: The relative duration of time with SpO₂ within the target range of 92 to 96% is greater in the PCLC compared with manual control (MC) group.

Secondary effectiveness for superiority: The relative duration of time with SpO₂ within the target range of 92 to 96% when FiO₂ > 21% and

SpO₂ ≥ 92% when FiO₂ = 21%, as measured by the relative duration, is greater in the PCLC compared with manual control (MC) group.

[figure not shown]
Primary safety: The use of PCLC to maintain the SpO₂ level at or above 88%, as measured by relative duration of time, is not inferior to the manual control (MC).

Population:

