12. STATISTICAL CONSIDERATIONS

12.1 Sample size

12.1.1 Primary Efficacy objective:

The primary efficacy endpoint is the relative duration of time where SpO₂ remains between 92 and 96% (inclusive). This will be obtained from continuously monitoring the subjects SpO₂ level throughout the study period such that at least 12 hours of monitoring data are available for each subject. The difference in the average amount of time will be the basis for the efficacy outcome comparison between the two ventilatory strategies.

To assess power for this objective the sample size calculation is based on preliminary data estimating the relative duration of time that SpO₂ remains between 92 and 96% (inclusive). To determine the noninferiority margin, the guidelines provided by FDA were followed (<http://www.fda.gov/downloads/drugs/guidancecomplianceregulatoryinformation/guidances/ucm202140.pdf>). From our preliminary data, the relative duration of time in which the SpO₂ remained between 92 and 96% in a four hour time interval for the MC group was 0.30 with 95% CI (0.23, 0.38). Following the guideline mentioned above we used half of the lower confidence bound to be the margin of non-inferiority (i.e. 0.12, which is equivalent to 7.2 minutes per hour) From our preliminary data, the SD for the MC and PCLC group was 0.33 and 0.23 respectively. Assuming a noninferiority margin of 0.12, a sample size of 91 subjects per group will achieve 80% power with a 2.5% one-sided significant level when the true difference between the group means is assumed to be zero. Allowing a 15% attrition rate for potential withdrawal of subjects the required sample size is 105 per group.

12.1.2 Primary Safety objective:

The primary safety endpoint is the relative duration of time with SpO₂ <88% over the study period. This will be observed by continuously monitoring each subject's SpO₂ level throughout the study period such that at least 12 hours of monitoring data are available for each subject. From our preliminary data the observed relative time where SpO₂ <88% was 0.004 and 0.002 for the MC and PCLC group respectively. The proposed sample size of 105 per group will allow us to conclude non-inferiority with a margin of 0.004 (which is equivalent to 15 seconds/hr) with 95% power with a 2.5% one-sided significant level.

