12.2 Statistical Analysis

For the primary outcomes, the intent-to-treat (ITT) population will be used for all efficacy and safety analyses. All subjects that were randomized and started the assigned ventilation strategy protocol will be included in the ITT. All summary tables for quantitative parameters will display mean, standard deviation, median, interquartile range, and range (minimum and maximum), as well as number of missing data (if relevant). All summary tables for qualitative parameters will display counts, percentages and number of missing data if relevant. Baseline characteristics will be described using the ITT population. Demographics, medical history and other baseline variables will be summarized as appropriate to the type of data. The primary effectiveness outcome will be defined as the proportion of time during the 12 hour monitoring period that the subject's SpO₂ levels were within the target range relative to the actual total monitoring time (which is targeted to be 12 hours for all subjects). By using the proportion of time instead of the actual time, we are able to normalize the outcome based on the total amount of monitoring time available. We will assess normality of the response variables within each of the two groups by visual inspection of the histograms and box plots and by performing the test for normality of data using the Shapiro Wilk test. If the assumption of normality for the primary effectiveness outcome does not seem tenable, we will use the arcsine square root transformation which is recommended to normalize skewed percentage data. A one-sided lower 97.5% confidence interval will be calculated for the difference between the two monitoring strategy groups (PCLC minus MC) in terms of the effectiveness outcome (duration where SpO₂ remains between 92 and 96% relative to the total monitoring time) and the lower limit will be compared to the noninferiority margin of 0.12. Similar analyses will be conducted for the secondary effectiveness outcome with the only difference being the way the duration is calculated for the secondary effectiveness outcome. For this analysis, the target duration will be calculated as amount of time that SpO₂ remains between 92 and 96% when FiO₂ > 21% and SpO₂ ≥ 92% when FiO₂ = 21%. The safety outcome (duration where SpO₂ remains above 88% relative to the total monitoring time) will be assessed using a one-sided lower 97.5% confidence interval and the lower limit will be compared to the non-inferiority margin of 0.004. If non-inferiority is established for an endpoint, we will proceed in conducting a superiority test and will compare the lower confidence limit to 0.

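### The arcsine-square-root fallback for the primary effectiveness test has no margin, back-transformation or stated scale, yet its limit is still compared with the raw-scale 0.12 and with 0

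*Combined protocol and SAP*

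**What the plan says.** Section 12.1.1 fixes the effect measure: "The difference in the average amount of time will be the basis for the efficacy outcome comparison between the two ventilatory strategies". The margin is in the same raw units ("i.e. 0.12, which is equivalent to 7.2 minutes per hour"), and the sample size uses raw-scale spreads: "From our preliminary data, the SD for the MC and PCLC group was 0.33 and 0.23 respectively".

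Section 12.2 has normality judged from histograms, box plots and a Shapiro-Wilk test, with no stated threshold. If normality looks untenable for the primary effectiveness outcome, "we will use the arcsine square root transformation which is recommended to normalize skewed percentage data". The next sentence describes a one-sided 97.5% lower limit for PCLC minus MC, and "the lower limit will be compared to the noninferiority margin of 0.12". If non-inferiority is shown, "we will proceed in conducting a superiority test and will compare the lower confidence limit to 0". The secondary effectiveness outcome is to be analysed in a similar way. For safety, "the lower limit will be compared to the non-inferiority margin of 0.004"; no transformation is mentioned there.

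The Protocol Summary makes the effectiveness test decisive: "Demonstration of non-inferiority for both the effectiveness and safety endpoints is required for study success".

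**The concern.** A margin belongs to a scale. The value 0.12 has a clinical meaning as a difference in the proportion of time on target; on the arcsine-square-root scale it is a different and stricter requirement, and how much stricter depends on the control mean. The plan does not say whether the limit is computed on transformed or raw data, how it would be back-transformed, or what margin would apply after transformation. Two analysts following the text could run different primary tests on the same data.

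There is a second problem that converting the margin would not cure. A difference of 0 in arcsine means is the same null as a difference of 0 in raw means only if the two distributions have suitably matching shapes. The plan expects the arms to differ in spread, so equal raw means can give unequal arcsine means, and the superiority test is then shifted.

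The fallback is also likely to be used. The planning values for manual control are a mean of 0.30 and an SD of 0.33 on an outcome bounded by 0 and 1. With the SD above the mean, the distribution cannot be close to normal.

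**Working it through.** **Inputs, all from section 12.1.1.** MC mean 0.30 (95% CI 0.23 to 0.38, 4-hour data); SDs 0.33 (MC) and 0.23 (PCLC); margin 0.12; 91 per group; 80% power; one-sided 2.5%; true difference 0.

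**1. Reproduce the plan's sample size on the raw scale.** Root-mean-square SD = √[(0.33² + 0.23²)/2] = √0.0809 = 0.2844. Then n = 2 × 0.0809 × (1.960 + 0.842)² / 0.12² ≈ 88.2, so 89 per group; a noncentral t calculation gives 90. The plan states 91. The design is therefore powered on the raw difference.

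**2. Convert the margin.** Let g(p) = arcsin√p.

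- Raw 0.12 at an MC mean of 0.30: g(0.30) − g(0.18) = 0.5796 − 0.4381 = 0.1415 on the arcsine scale.
- Arcsine 0.12 at an MC mean of 0.30: 0.30 − sin²(0.5796 − 0.12) = 0.30 − 0.197 = 0.103 raw, and 0.103 × 60 = 6.2 minutes per hour.
- The raw equivalent of arcsine 0.12 at other MC means is 0.092 at 0.23, 0.112 at 0.38, 0.119 at 0.50 and 0.115 at 0.70.

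No single arcsine margin reproduces 7.2 minutes per hour. This step needs no assumption about the distribution of subject values.

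**3. Operating characteristics by simulation.** Assumptions: subject values follow beta distributions matched to the stated mean and SD; 91 per arm; Welch one-sided 97.5% lower limit; MC SD 0.33 and PCLC SD 0.23 unless stated; 40,000 trials per scenario. Equal raw means are assumed, so a PCLC mean of 0.30 is not a figure from the plan. Limits on both scales are compared with −0.12 and 0.

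| Equal raw mean | False superiority, arcsine | False superiority, raw | NI power, arcsine | NI power, raw |
|---|---|---|---|---|
| 0.23 | 16.0% | 3.0% | 84% | 80% |
| 0.30 | 10.9% | 2.7% | 81% | 80% |
| 0.38 | 6.3% | 2.6% | 76% | 80% |
| 0.50 | 2.6% | 2.6% | 65% | 81% |
| 0.70 | 1% or less | about 2.5% or less | 31% | 81% |

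- *Cause of the superiority inflation.* At mean 0.30 the arcsine means are 0.5092 (MC) and 0.5471 (PCLC), a difference of +0.038 with no raw difference. With equal SDs the arcsine rate returns to 2.5–2.6%, so the unequal spread is the cause and not the margin.
- *Shape and sample size.* A logit-normal shape gives 9.7% at mean 0.30. With 105 per arm (beta) the rate is 11.8%.
- *False non-inferiority at a true −0.12.* It is 0.1–1.3% on the arcsine scale for MC means of 0.23–0.70, against 2.1–2.8% raw. The arcsine test is conservative here.
- *Why NI power looks unaffected at 0.30.* The +0.038 shift offsets the stricter margin. With both SDs at 0.28 (mean 0.30), power is 62% arcsine against 82% raw; with both at 0.33, 45% against 68%.
- *Conflicting verdicts.* The two scales give opposite NI verdicts on the same data in about 3% of trials at mean 0.30, 16% at 0.50, and 20% at mean 0.30 with both SDs at 0.28.
- *Does the transformation work?* At means 0.23–0.38, Shapiro-Wilk (5%, either arm) rejects in every trial before transformation and in at least 99.7% after it.

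**The case against.** The best counter-argument is textual. The interval sentence in section 12.2 describes the outcome in parentheses as time on target relative to monitoring time, which is the raw proportion, and compares it with a raw margin. On that reading the interval stays on the raw scale and none of the arcsine error rates arise. But the parenthesis only names the endpoint, and if the interval is always raw, the transformation announced just before it has no role. The scale is unclear either way.

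Several limits on the size of the problem do stand:

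- At the planning mean and SDs, NI power is the same on both scales and the verdicts rarely differ. If PCLC is better by the 0.14 given in section 12.1 (0.44 against 0.30), both scales declare NI in essentially every trial.
- The superiority inflation needs low means and a clearly wider spread under manual control. With SDs of 0.26 and 0.23 at mean 0.30 it is 4.3%; at a mean of 0.50 it is gone, and above that it reverses. Superiority is not required for study success.
- The planning moments are 4-hour values. Here both arms share a 94% target over 12 hours, so mean and spread may differ. For a beta arm with mean 0.60 and SD 0.20, Shapiro-Wilk rejects in 49% of samples before transformation and 7% after. That the fallback will be triggered, and that it will fail to normalise, are statements about the planning values.
- The missing minus sign is a drafting slip with clear intent.

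**Conclusion.** The concern holds. The margin is defined, justified and powered on the raw scale, and the fallback then changes the outcome's scale while keeping the same two thresholds. Followed as written, with the interval on the transformed outcome, the plan no longer tests the stated difference in mean relative duration.

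For non-inferiority the danger is an undefined test and lost power, not a false claim: power is 65% at equal means of 0.50 and 31% at 0.70, against 81% raw, and unchanged at 0.30. For superiority the error rate can reach about 6–16% across the plan's own interval for the MC mean (0.23–0.38), provided the SDs differ as planned. These rates rest on an assumed beta shape and equal raw means; the margin conversions do not. This should be fixed before unblinding, because a scale chosen afterwards could decide the result.

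**What to change.** In section 12.2:

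- Name the raw difference in mean proportion (PCLC minus MC), with an unequal-variance t interval, as the primary effectiveness analysis whatever the normality checks show. Add a bootstrap interval as a check.
- Keep the arcsine-square-root analysis, if wanted, as a sensitivity analysis with no margin comparison.
- Apply the same to the secondary effectiveness outcome.
- State the rule with its signs: non-inferiority if the lower 97.5% limit exceeds −0.12 (effectiveness) or −0.004 (safety); superiority if it exceeds 0. The sign is the only part of this point that touches safety.

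A transformed margin or a defined back-transformation would settle the non-inferiority ambiguity, but not the shift in the superiority test caused by unequal spread.

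The cost is a few sentences, with no extra patients or data. In the same simulation at mean 0.30, the raw Welch limit gave 2.7% false superiority and 80% NI power; a raw percentile bootstrap (1,500 trials, 1,000 resamples) gave 2.9% and 80%.

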Therefore for this study we are proposing to enroll a total of 210 subjects to test the noninferiority hypothesis for both our primary safety and effectiveness outcomes. For all sample size estimates, PASS version 12 (PASS, NCSS LLC., Utah, US) was used.

If noninferiority is demonstrated, the proposed sample size also has 80% power to test for the superiority of the LLC group versus MC group both in terms of the primary effectiveness and safety outcomes if the true difference between ventilatory strategies is at least 0.14 (which is equivalent to 8.2 minute per hour) for the primary efficacy endpoint and is at least 0.003 (which is equivalent to 10 second per hour) for the primary safety endpoint.

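### The superiority gate in section 12.2 works endpoint by endpoint, unlike the both-endpoints success rule in section 1, and up to three superiority tests run at one-sided 2.5% with no order or adjustment

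*Combined protocol and SAP*

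**What the plan says.** Section 1 sets out a staged plan, "We plan to conduct a 2-state statistical test: non-inferiority followed by a superiority test", and then the success rule: "Demonstration of non-inferiority for both the effectiveness and safety endpoints is required for study success". Its hypothesis list has superiority statements for primary and secondary effectiveness. For safety it has only a non-inferiority statement.

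Section 12.2 sets the tests:

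- Primary effectiveness uses a one-sided 97.5% lower confidence limit for PCLC minus MC, against a margin of 0.12.
- On the second endpoint: "Similar analyses will be conducted for the secondary effectiveness outcome".
- Safety "will be assessed using a one-sided lower 97.5% confidence interval and the lower limit will be compared to the non-inferiority margin of 0.004".
- The step to superiority follows: "If non-inferiority is established for an endpoint, we will proceed in conducting a superiority test", and the analysis "will compare the lower confidence limit to 0".

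The closing paragraph of section 12.1 makes superiority conditional on non-inferiority without naming the endpoint. It claims 80% power for superiority "both in terms of the primary effectiveness and safety outcomes", at differences of 0.14 and 0.003. The documents state no testing order, alpha allocation or multiplicity method across these tests.

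**The concern.** There are two linked problems.

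**The gates differ.** Section 1 needs both primary endpoints to be non-inferior. Section 12.2 lets one endpoint open its own superiority test. A trial that failed on time below 88% could still report PCLC as superior on time in range, following the analysis section to the letter.

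**The superiority claims form an uncontrolled family.** Each uses the full one-sided 2.5%. Going from non-inferiority to superiority with one interval protects the error within an endpoint, but not across two or three endpoints. The documents also disagree on whether safety superiority is a formal hypothesis: it is absent from section 1, powered in 12.1 and tested in 12.2.

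At stake is how far any superiority claim can be relied on. If the gate or the order is settled after the data are seen, the claim is weakened whatever its p-value.

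**Working it through.** **1. The plan's own figures.** Inputs from 12.1.1: SD 0.33 (MC) and 0.23 (PCLC), margin 0.12, one-sided 2.5%, 80% power, true difference 0.

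- Average-variance SD = √((0.33² + 0.23²)/2) = 0.2844.
- n = 2 × 0.2844² × (1.960 + 0.842)² / 0.12² = 88.2, so 89 per group. A t-based calculation gives 90. The plan states 91, where power is 80.8–81.2%. The figure reproduces within 2 subjects.
- Superiority: with n = 91 and SD 0.33 in both arms (an assumption), the difference detectable with 80% power is 2.802 × 0.33 × √(2/91) = 0.137, or 8.2 minutes per hour, as in 12.1. With SDs 0.33 and 0.23, power at 0.14 is 91.3%. The stated superiority power thus matches an unadjusted one-sided 2.5% test, so no multiplicity allowance is built in.

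**2. The gates side by side.**

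| Place | Condition for success or superiority |
|---|---|
| Section 1 | Success: non-inferiority on effectiveness and on safety |
| Section 12.1, last paragraph | Superiority: non-inferiority shown, endpoint not named |
| Section 12.2 | Superiority: non-inferiority on that one endpoint |

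**3. The endpoint-wise gate gives no protection across endpoints.** A lower limit above 0 is automatically above −0.12 (or −0.004 for safety). Passing superiority on an endpoint therefore implies passing its gate, and the gate removes no false superiority claims.

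**4. Chance of at least one false superiority claim, all true differences zero.** For k independent tests it is 1 − 0.975^k. With correlation it is 1 − P(all Z ≤ 1.960) under a multivariate normal. The correlations are assumptions.

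| Tests | Assumed correlation | Error |
|---|---|---|
| Two primaries | 0 | 1 − 0.975² = 4.9% |
| Two primaries | 0.5 | 4.5% |
| All three | 0 throughout | 1 − 0.975³ = 7.3% |
| All three | 0.5 throughout | 6.3% |
| All three | 0.8 between effectiveness endpoints; 0 / 0.3 with safety | 6.3% / 6.1% |
| All three | 0.95 between effectiveness endpoints; 0 / 0.3 with safety | 5.6% / 5.4% |

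The 0.8–0.95 rows are the more plausible. The two effectiveness endpoints are the same quantity whenever FiO₂ exceeds 21% and differ only at 21%, and entry requires FiO₂ of at least 40% (section 5.3).

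**5. How often effectiveness superiority would coincide with failed safety non-inferiority.** Section 12 gives no safety SD. I assume the values from the earlier crossover trial (section 3.2.2) divided by its 240 minutes: 2.64/240 = 0.0110 (MC) and 1.37/240 = 0.0057 (PCLC). I also assume independent endpoints, 105 per group and a true effectiveness difference of 0.14.

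- Standard errors: effectiveness √((0.33² + 0.23²)/105) = 0.0393; safety √((0.0110² + 0.0057²)/105) = 0.00121.
- P(effectiveness superiority) = Φ(0.14/0.0393 − 1.960) = 94.6%.
- True safety equal: P(safety non-inferior) = Φ(0.004/0.00121 − 1.960) = 91.1%. Joint probability 0.946 × 0.089 = 8.4%.
- PCLC worse by exactly the margin: 0.946 × 0.975 = 92.2%.
- PCLC better by 0.002, the preliminary difference in 12.1.2: about 0.1%.

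The route matters mainly when PCLC is not better on safety.

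**6. What each part of a fix achieves.** These are simulated at zero true differences over effectiveness correlations of 0–0.95 and safety correlations of 0 or 0.3. A gate on both primary non-inferiority tests, with three unordered superiority tests behind it, leaves 5.0–6.5%. The same gate plus a fixed sequence led by primary effectiveness gives 2.3–2.5%. Both parts are needed.

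**The case against.** The strongest reply is that the trial's confirmatory conclusion is already protected. Requiring both non-inferiority tests to pass holds the study-success error at or below 2.5% with no adjustment, and moving from non-inferiority to superiority within an endpoint needs none either. Superiority does not define success. This stands. A reader might infer that the trial's error rate as a whole is uncontrolled; the documents do not support that.

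A second reply is that the gate was meant to be joint. Section 1 describes stages, and the superiority paragraph in 12.1 directly follows one about testing non-inferiority on both outcomes. A reader might infer from 12.2 that the trial could be called a success after failing on safety. Section 1 rules that out. What remains is that the operative analysis sentence sets its gate per endpoint, so the sections need reconciling.

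Third, 7.3% assumes independence between two endpoints that overlap by construction. This also stands, so it is an upper case and not the expected figure. Every case worked here still exceeds 2.5%.

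Finally, the testing order is a matter of choice. That is correct: several orders, or an alpha adjustment, would serve, provided one is stated beforehand.

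**Conclusion.** The point holds for the superiority claims only. The gate in 12.2 does not match the success rule in section 1. Up to three superiority tests run at 2.5% each with no order or adjustment, and safety superiority has no settled status. The chance of at least one false superiority claim is roughly twice the nominal 2.5%: about 4.5–4.9% for the two primary endpoints and about 5.4–6.3% for all three under the more plausible correlations, with 7.3% as the ceiling under independence. These figures rest on assumed correlations and approximate normality. The step 5 probabilities also rest on a borrowed safety SD. The change should be made before data are seen, but the primary non-inferiority conclusion does not depend on it.

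**What to change.** In 12.2, replace the sentence that opens superiority with wording such as: *Superiority will be tested only if non-inferiority is shown for both primary endpoints. Tests will then follow a fixed sequence at one-sided 2.5%, starting with primary effectiveness and stopping at the first failure.* One workable order is primary effectiveness, secondary effectiveness, then safety if it is kept as a formal hypothesis. Make the condition in the last paragraph of 12.1 match. Either add safety superiority to the section 1 hypotheses or label it descriptive in 12.1 and 12.2.

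An alpha adjustment behind the same joint gate is an alternative. Bonferroni over three tests (2.5%/3 = 0.83% each) gives power at a difference of 0.14 of 68.0% (SD 0.33 in both arms, n = 91), 82.3% (SDs 0.33 and 0.23, n = 91) or 88.0% (same SDs, n = 105).

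Cost: because this is a combined protocol and SAP, a wording amendment with IRB review under section 14.2. With a fixed sequence, each test keeps its 2.5% and the sample size does not change, but a later superiority claim is lost if an earlier test fails.

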4.2 Secondary Objectives

Four additional safety related question will be addressed:

1. The rate of serious adverse events related to the PCLC is not different than those attributed to the MC group
2. The rate of serious adverse events not related to the PCLC is not different than those attributed to the MC group
3. The number of missed diagnosis attributed to the PCLC is not different than those attributed to the MC group
4. The rate of device related adverse events related to the PCLC is not different than those attributed to the MC group.

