
For the analysis of secondary safety outcome, data point estimates will be reported with 95% confidence intervals followed by a Fisher's Exact Test at the 5% level of confidence. Specifically the percentage of subjects reporting at least one adverse event (i.e serious, any device related, etc.) will be calculated for each group and compared using Fisher's Exact Test. The relative risk of each adverse event with the corresponding two-sided 95% confidence interval will be presented.

Missing data: The primary analysis is an intent to treat analysis. In order to minimize the possibility of missing data, the total duration of monitoring will be extended for each subject as needed in order to collect at least 12 hours of evaluable data. As a sensitivity analysis, the primary outcome measure also will be calculated as the relative time the subject was on target compared to the total amount of time they were on manual or closed-loop control. Therefore each subject should have the outcome measurement. The amount of missing data is expected

to be low based on past experience with subject retention. However there is a very low probability that some subjects may die before completing 12 hours of monitoring on the device. In this case, the relative duration will be derived by using the total duration of time the subject was on target relative to the monitoring time until they died. If a subject does not have 12 hours of monitoring data on the device due to a reason other than death, we will conduct sensitivity analysis by assuming different scenarios. In a worst case scenario, the primary outcome will be computed as the total time in the target range divided by 720 minutes. In a best case scenario, the primary outcome will be computed as the total time in the target range divided by the total amount of time the subject was observed (i.e. <720 minutes). In the event of missing data on the primary safety and efficacy outcomes (except where the subject died), the reason for the missing values will be explored, and the pattern of missing values (e.g. missing at random, missing completely at random) will be evaluated. In addition, analyses excluding those subjects without 12 hours of monitoring will also be conducted as sensitivity analyses.

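### Four secondary safety objectives claim no difference between arms, but the only test is a 5% Fisher's exact test of equality with no margin, so a non-significant result cannot support them

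*Combined protocol and SAP*

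**What the plan says.** Section 4.2 lists four safety questions, each worded as an absence of difference:

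- "The rate of serious adverse events related to the PCLC is not different than those attributed to the MC group"
- "The rate of serious adverse events not related to the PCLC is not different than those attributed to the MC group"
- "The number of missed diagnosis attributed to the PCLC is not different than those attributed to the MC group"
- "The rate of device related adverse events related to the PCLC is not different than those attributed to the MC group"

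Section 9.1.2 lists the same four items as secondary safety variables, without a claim attached. For the secondary safety outcome, section 12.2 plans that "data point estimates will be reported with 95% confidence intervals followed by a Fisher's Exact Test at the 5% level of confidence". It adds that "the percentage of subjects reporting at least one adverse event (i.e serious, any device related, etc.) will be calculated for each group", and that the groups are compared on this percentage by Fisher's test. It then requires estimation: "The relative risk of each adverse event with the corresponding two-sided 95% confidence interval will be presented".

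The primary safety outcome, time at adequate SpO₂, is handled differently. There "the lower limit will be compared to the non-inferiority margin of 0.004". Section 12.1 sizes the trial on the two primary SpO₂ outcomes only. It gives no expected rate, margin or power for serious adverse events, device-related events or missed diagnoses.

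**The concern.** A claim that two rates do not differ is an equivalence or no-excess-harm claim. Fisher's test takes equality as its null, so the statement the sponsor wants to make is the hypothesis under test. Failing to reject it shows only that the data did not contradict it, and small event counts make that outcome likely whatever the truth. The fewer the events, the easier the claim becomes to make.

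The plan uses the sound approach for its primary outcomes, where a confidence limit is set against a margin. It does not carry this over to the adverse-event and missed-diagnosis objectives, which are the planned between-arm comparisons of clinical harm beyond SpO₂. Nor does it say which result would support the 4.2 wording, so that choice is left until after the data are seen.

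**Working it through.** **Inputs.** 105 per arm, 1:1 allocation (5.2, 5.6.1). Fisher's exact test at 5% on subjects with at least one event (12.2); sidedness is not stated, so two-sided is assumed. The MC event risk is not given and is assumed over 1% to 20%. The nearest figure in the documents is the one serious event in the earlier 95-patient crossover study (3.2.2), 1/95 = 1.1%. That study used two 4-hour periods, so the figure is only a rough guide.

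**The plan's own figure.** Section 12.1.1 gives 91 evaluable per group for the efficacy margin of 0.12, with SDs 0.33 and 0.23. The normal approximation is (1.96 + 0.842)² × (0.33² + 0.23²) / 0.12² = 7.849 × 0.1618 / 0.0144 = 88.2, so 89. A t-based calculation gives 80.8% power at 91. Then 91 × 1.15 = 104.7, so 105. The stated size is reproduced, but it says nothing about the secondary safety tests.

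**Chance that a true doubling is non-significant.** This is 1 − Σᵢ Σⱼ Bin(i; 105, 2p) · Bin(j; 105, p) · 1{Fisher p(i, j) ≤ 0.05}, where p is the MC risk.

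| MC risk | PCLC risk | Non-significant |
|---|---|---|
| 1% | 2% | 99.3% |
| 2% | 4% | 95.2% |
| 5% | 10% | 79.8% |
| 10% | 20% | 54.4% |
| 20% | 40% | 13.7% |

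Detecting 5% against 10% with 80% power would need about 474 per arm (continuity-corrected).

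**Events absent on MC.** With 0 MC events, PCLC needs 6 for p ≤ 0.05. If the true MC risk is zero, the miss rate is P[Bin(105, p) ≤ 5], where p is the PCLC risk: 57% at 5% and 90% at 3%.

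**What particular results would show, PCLC first, out of 105 each.**

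- 10 vs 5: Fisher p = 0.28; relative risk 2.0 (95% CI 0.71 to 5.65).
- 13 vs 5: p = 0.082; relative risk 2.6 (0.96 to 7.03); Newcombe risk difference −0.1 to +15.7 points.
- 5 vs 0: p = 2 × C(105,5)/C(210,5) = 0.060; relative risk undefined. The Wilson limits are 2.05% to 10.67% for 5/105 and 0 to 3.53% for 0/105. The Newcombe lower limit is 4.76 − √(2.71² + 3.53²) = +0.3 points, and the upper limit is 4.76 + √(5.90² + 0²) = +10.7 points.

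**What 105 per arm can exclude when the arms are equal (Newcombe upper limit).** For 5 vs 5 it is √(5.90² + 2.71²) = 6.5 points. In the same way, 0 vs 0 gives 3.5, 10 vs 10 gives 8.3 and 21 vs 21 gives 10.8 points.

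**The case against.** The strongest reply is that estimation is already planned and comes first: point estimates with 95% intervals, then Fisher's test, then a relative risk with its interval. For 13 vs 5 that interval, 0.96 to 7.03, would show a careful reader that harm is not excluded. Section 4.2 also introduces the items as questions to be addressed, and 12.2 nowhere says that p > 0.05 will be reported as no difference. These points stand, and they limit the concern. They do not remove it: no conclusion is tied to any interval, the only wording on offer is that of 4.2, and the relative risk fails where MC has no events, which is plausible for device-related events.

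A reader might infer that the trial would report a doubling of serious adverse events as no difference about 80% of the time. The documents do not support that. The figure needs an assumed 5% MC risk, which they never give, and the reporting rule is an inference.

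A reader might also infer that the trial's overall safety claim rests on these tests. It does not. The aim in the protocol summary is expressed in terms of SpO₂ control, and success requires non-inferiority on the two primary endpoints, which have margins. Patient protection does not depend on Fisher's test either: the DSMB reviews all serious events whatever their cause (9.6.4), and the medical monitor can terminate the study (10.1).

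**Conclusion.** The concern holds as a mismatch between objective and analysis. The four objectives in 4.2 cannot be supported by a non-significant Fisher test, and the plan gives no other criterion. How misleading a non-significant result would be depends on event rates the documents do not state. At 105 per arm, the chance of missing a true doubling runs from about 99% at an MC risk of 1% to about 14% at 20%, and is 80% or more at 5% or below. This assumes a two-sided test, independent arms and all 105 subjects per arm counted. The effect is confined to the secondary safety conclusions; the primary analyses and the criterion for study success are untouched.

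**What to change.** 1. In 4.2, replace the no-difference wording in each item with an aim to estimate the difference between PCLC and MC in that outcome.
2. In 12.2, add the risk difference (PCLC minus MC) with a two-sided 95% Newcombe interval beside the planned relative risk. It remains defined when one or both arms have no events.
3. Base the secondary safety conclusions on the upper limit of that interval, reported as the largest excess not excluded.
4. State that the Fisher p-value is descriptive and that p > 0.05 will not be taken as evidence of no difference.
5. State in advance what 105 per arm can exclude when the arms are equal: about 3.5 percentage points with no events, 6.5 at about 5%, 8.3 at about 10% and 10.8 at 20%.

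The cost is a wording change in two sections and one more interval per table, with no new data or patients. The downside is that the sponsor can no longer state that these events do not differ between arms, and must say how large an excess remains possible.
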